5.3. Lifestyle Restrictions

Participants in the two antibiotic groups will have certain lifestyle restrictions with which they will need to comply and that the site staff will need to remind them on an on-going basis. In addition, for Group 1A and 2A participants, meals served during PK sessions need to observe these same limitations. Details of these restrictions are provided below.

5.3.1. Meals and Dietary Restrictions

5.3.1.1. Precautions for Participants Taking Ciprofloxacin or Doxycycline

Participants in Groups 1 and 2 should be informed that these antibiotics may be taken with or without food, but antacids containing magnesium or aluminum and multivitamin/supplement preparations with calcium, zinc or other metals, eg, iron, should be taken at least two hours before or six hours after antibiotic administration. Furthermore, the same schedule should be used for the consumption of dairy products (like milk or yogurt) or calcium-fortified juices and the timing of antibiotic dosing since absorption of antibiotic may be significantly reduced by consumption of dairy products. However, these antibiotics may be taken with a meal that contains these products. In addition, participants in Group 2 should avoid taking bismuth subsalicylate (Pepto Bismol[®]) within 2-3 hours of their doxycycline dose.

Participants should also be asked to limit their consumption of caffeine to 400 mg/day (equivalent to about 4 cups of coffee).

5.3.1.2. Special Meals for Participants on Days with PK Sessions

On their PK session days [Days 4, 8, 31 and 35 for Group 1A (ciprofloxacin) and Days 2, 8, 32 and 38 for Group 2A (doxycycline)], participants are to be provided a non-dairy breakfast, 30 to 60 min prior to dosing. This is to be followed over the course of the day with a light lunch and a light dinner/snack.

5.3.2. Activity Restrictions

Participants should be asked to limit their time in the sun and to avoid the use of sunlamps and tanning beds. Ciprofloxacin and doxycycline increase the sensitivity of the skin to the ultraviolet radiation both from the sun and from artificial sources such as sunlamps and tanning beds. All such exposures while on these medications can result in severe sunburns, blisters or swelling of the skin.

Participants should be reminded to avoid sun exposure but if they must go out to avoid the high UV hours of 10 am to 2 pm, to wear sunscreen and protective gear (hats, sunglasses and protective clothes) when they do go outside. If they develop any of the signs or symptoms of sunburn while on antibiotic, participants must be instructed to notify the site staff.

Participants in Group 1 should be advised against engaging in strenuous physical activity as this may independently increase the risk of tendon rupture from ciprofloxacin.

During each PK session, participants should remain in a seated or semi-recumbent position for 2 hours post-dose and then maintain a light activity level throughout the course of the day.

AV7909 Anthrax Vaccine

IND 014451

Protocol EBS.AVA.210, Version 3.0 (28 October 2019)

5.4. Screen Failures

A screen failure is a participant from whom informed consent is obtained and documented in writing, but who is not subsequently randomized to study treatment. Reasons for screen failure are to be recorded in the electronic case report forms (eCRFs).

All screening procedures must occur 2 to 28 days before the Day 1 study visit, at which time participants are allocated to a treatment group. During the initial Screening visit, the Principal Investigator (PI) or designee will confirm, by documentation of the evaluation, any transient acute condition that may affect the participant's Screening clinical laboratory results (which should meet the criteria specified in [Exclusion criterion 1](#)). The clinical laboratory assessment can be performed at the same visit or delayed, allowing time for resolution of the transient acute condition (eg, delayed screening until resolution of febrile illness, delayed urine occult blood in a menstruating woman). The clinical laboratory testing for Screening will not be performed more than twice (one initial and one repeat test for a total of two times). If the laboratory results are abnormal due to a processing or handling error, the test will be repeated without counting towards the not-to-exceed total of twice performed.

Participants who are screen failures are permitted to be rescreened one time (only) according to the PI's discretion. In the event that the participant is rescreened for trial participation, a new informed consent form (ICF) must be signed. For example, if there are any delays between Screening and enrollment that cause eligible participants to fall outside the Screening window, these participants may be re-consented and rescreened. Participants who complete the rescreening and are randomized in the study will not be considered screen failures.

AV7909 Anthrax Vaccine

IND 014451

Protocol EBS.AVA.210, Version 3.0 (28 October 2019)

6. TREATMENTS

6.1. Treatment Administration

6.1.1. AV7909 Description

AV7909 is a preformulated, sterile, milky-white suspension for IM injection consisting of the AVA drug substance (AVA) and CPG 7909 adjuvant. All participants will receive one dose of AV7909 0.5 mL IM, consisting of 0.5 mL AVA and 0.25 mg CPG 7909, on Day 8 and one dose IM on Day 23.

The AV7909 vaccine, manufactured by [REDACTED], will be supplied in 6 mL (nominal fill volume) clear borosilicate glass multi-dose vials with rubber stoppers and flip-top aluminum seals for storage. A single vial is filled with approximately 6.1 mL. For purposes of this trial, only a single dose (0.5 mL) will be used from each vial.

Each vial will be labeled with the name, main constituents and volume of study product; route of administration; manufacturer name; characterization as “sterile” product and “multi-dose vial”; storage conditions; manufacturing (fill) date and lot number; and appropriate federal caution statement for investigational use product.

6.1.2. Ciprofloxacin Description

Ciprofloxacin hydrochloride, USP, a fluoroquinolone, is a synthetic broad-spectrum antimicrobial agent for oral administration. It is the monohydrochloride monohydrate salt of 1-cyclopropyl-6-fluoro-1, 4-dihydro-4-oxo-7-(1-piperazinyl)-3-quinolinecarboxylic acid. It is a faintly yellowish to light yellow crystalline substance with a molecular weight of 385.8. Its empirical formula is $C_{17}H_{18}FN_3O_3 \cdot HCl \cdot H_2O$.

Ciprofloxacin will be provided as tablets of ciprofloxacin hydrochloride at strength of 500 mg ciprofloxacin equivalent. The manufacturer and exact formulation, ie, excipients, and format for the tablets will be specified in the Pharmacy Manual.

6.1.3. Doxycycline Description

Doxycycline hyclate, USP, is a broad-spectrum antibiotic synthetically derived from oxytetracycline. The chemical designation is 4-(Dimethylamino)-1,4,4a,5,5a,6,11,12a-octahydro-3,5,10,12,12a-pentahydroxy-6-methyl-1,11-dioxo-2-naphthacene-carboxamide monohydrochloride, compound with ethyl alcohol (2:1), monohydrate. Doxycycline is a light-yellow crystalline powder. The hyclate has a molecular weight 1025.9 with an empiric formula of $(C_{22}H_{24}N_2O_8 \cdot HCl)_2 \cdot C_2H_6O \cdot H_2O$.

Doxycycline will be provided as tablets of doxycycline hyclate at strength of 100 mg doxycycline equivalent. The manufacturer and exact formulation, ie, excipients, and format for the tablets will be specified in the Pharmacy Manual.

AV7909 Anthrax Vaccine

IND 014451

Protocol EBS.AVA.210, Version 3.0 (28 October 2019)

6.1.4. Administration of AV7909

AV7909 will be administered to all participants in all groups as a 0.5 mL IM vaccination in alternate arms on Days 8 and 23. Vaccinations will be administered in the clinic by authorized personnel once AEs have been assessed, vitals have been taken and a symptom-directed PE conducted. Females who have not demonstrated an FSH level >30 mIU/mL must also pass a urine pregnancy test (see [Section 8.3.2](#)).

Participants in Groups 1A and 2A will receive their first vaccination after the 12-hour PK sample in the evening of Day 8, and their second vaccination on Day 23. Site personnel who administer the vaccine should be trained in the early recognition of symptoms of anaphylactic reactions, a rare but potentially serious reaction to parenteral injections.

Sites should be prepared to treat participants experiencing clinically significant dyspnea or hypotension, wheezing or generalized urticarial reactions. Appropriate medical therapy for anaphylaxis should be administered, if indicated, which should include IM or subcutaneous epinephrine 1:1000, and may include corticosteroids, diphenhydramine, bronchodilators, intravenous volume expansion, and/or oxygen. Participants will be evaluated and carefully monitored until complete resolution of any signs and symptoms, should they occur.

If a participant in Groups 1 or 2 has a moderate or severe illness and/or an oral temperature greater than 100.4°F within three days before vaccination 1, or any condition that, in the opinion of the Investigator, would render vaccination unsafe or would interfere with evaluations, these participants will be withdrawn from the study and will be considered ineligible for rescreening. These participants will be instructed to cease taking antibiotics but to continue with their e-diary for an additional 7 days beyond the day they ceased taking antibiotics at which point they will be asked to return to the site and complete the EWV procedures. If the reason for not receiving vaccine is an AE/SAE/AESI, the participants will be followed until the event has resolved, stabilized or the participant has been referred to another physician. These participants, having not received any vaccine, will not be included in the long-term follow-up nor will they have additional blood samples taken for TNA, TSH or autoantibodies.

Any participant in Group 3 who has a moderate or severe illness and/or an oral temperature greater than 100.4°F within three days before vaccination 1, or any condition that, in the opinion of the Investigator, would render vaccination unsafe or that would interfere with evaluations may be re-screened and re-randomized with the event which precluded vaccination being added to that participant's medical history. If such an event were to occur within three days of vaccination 2, the vaccination must be delayed but should still occur within the 1-day study window. Participants unable to receive vaccination 2 within the allowed study visit window will remain in the study and be followed for safety.

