3.2.2. Secondary Endpoints

Safety

- Incidence of AEs from the first dose of any IP through the Final Study Visit (Day 51 ± 1 d)
- Incidence of serious AEs (SAEs) from the first dose of any IP until the 12-month follow-up (Day 388 ± 14 d)
- Incidence of solicited systemic and injection site reactions reported in participant e-diaries following each vaccination
- Incidence of AESIs from the first dose of any IP until the 12-month follow-up (Day 388 ± 14 d)
- Incidence of clinical laboratory abnormalities

Pharmacokinetics and Immunogenicity

- AUC_{0-12h} and C_{max} for ciprofloxacin on Days 4 and 31 and for doxycycline on Days 2 and 32
- Geometric mean TNA 50% neutralizing factor (NF_{50}) values 2 weeks after the second vaccination (Day 37 ± 1 d)

AV7909 Anthrax Vaccine

IND 014451

Protocol EBS.AVA.210, Version 3.0 (28 October 2019)

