7.3. Individual Participants

All participants have the right to withdraw at any point during treatment without prejudice. The PI can also discontinue a participant from a trial at any time if medically necessary or for reasons of noncompliance.

Every attempt will be made to follow participants for safety for the entire duration of the trial through the Month 12 safety follow-up providing they have received at least one vaccination. Participants in Groups 1 and 2 who discontinue treatment prematurely for any reason after receiving the first dose of antibiotic but prior to receipt of the first vaccination will be encouraged to return to the clinic for the Early Withdrawal procedures minus the blood draws for autoantibodies, TSH and TNA. Participants who discontinue treatment prematurely for any reason after receiving the first vaccination will be encouraged to continue in the study for any

AV7909 Anthrax Vaccine

IND 014451

Protocol EBS.AVA.210, Version 3.0 (28 October 2019)

remaining study visits (for safety assessments only) and the safety follow-up phone calls at Months 3, 6, 9 and 12 (post-vaccination).

If a participant discontinues treatment and/or involvement in the study, the reason(s) must be fully evaluated and recorded appropriately in source documents and eCRFs. Reason for discontinuation of treatment and reason for withdrawal from the study are to be recorded separately on eCRFs. If the participant is being discontinued because of an AE, that AE will be indicated as the reason for discontinuation and/or study withdrawal.

Randomized participants who withdraw for any reason will not be replaced in this trial.

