9.2. Eliciting and Reporting Adverse Events

AEs (including SAEs and potential AESIs) reported spontaneously by the participant and/or in response to an open question from the PI or designee or revealed by observation (eg, during PE

AV7909 Anthrax Vaccine

IND 014451

Protocol EBS.AVA.210, Version 3.0 (28 October 2019)

or from a clinical test result) will be recorded on the AE eCRF if they occurred from the time of the first administration of any IP (Day 2 for Group 2, Day 4 for Groups 1 or Day 8 for Group 3) through Day 51 or EWV, regardless of causal association with the IP. AE reporting is required for any new observation presenting after the first receipt of any IP or for a deterioration of baseline condition (eg, increased severity/frequency). From the signing of the ICF until immediately before the administration of their first IP, only AEs resulting from a study-related procedure will be recorded on the AE eCRF; all other events reported in these time periods will be recorded as signs and symptoms on the Medical History eCRF. If there is any doubt as to whether a clinical or laboratory observation is an AE, the event will be considered an AE and recorded on the AE eCRF. After Day 51 and through the 12-month safety follow-up, AEs, SAEs (meeting definition per [Section 9.1.2](#)) and AEs assessed by the DSMB to be of autoimmune etiology (refer to [Section 8.5](#)), ie, AESIs, will be recorded on the AE eCRF.

Refer to the specific sections on clinical laboratory tests ([Section 8.3.2](#)), PEs ([Section 8.3.3](#)), vital signs ([Section 8.3.4](#)), and e-diary reactogenicity ([Section 8.3.5.1](#)) for details on AE reporting based on participant observation and clinical test results.

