9.3. Immediately Reportable Events

9.3.1. Principal Investigator's Responsibilities

The following events must be reported via email immediately (ie, within 24 hours of awareness), by the site PI or designee to [REDACTED]:

- Any SAE regardless of causal association with any IP
- Any potential AESI, ie, AE of autoimmune etiology (refer to the list of AESI terms in [Appendix B](#)) regardless of causal association with any IP (ie, ciprofloxacin, doxycycline or AV7909)
- Any pregnancy where conception occurred after first exposure to any IP (ie, ciprofloxacin, doxycycline or AV7909) and prior to 12 months after last receipt of either IP

The appropriate form (listed below) will be completed and sent by email to the following address:

[REDACTED]
[REDACTED]
[REDACTED]
[REDACTED]

For SAEs and AESIs, the Serious Adverse Event and/or Adverse Event of Special Interest Report Form will be completed (abbreviated hereafter SAE Report Form, AESI Report Form). Note that the SAE and AESI Report Form are not the same as the AE eCRF. Accompanying these forms will be source documentation or medical records (eg, discharge summary for hospitalizations, lab reports) which support a diagnosis. Participant identifiers (eg, individual's name, address, telephone number, social security number, medical record number, or hospital/laboratory number) must be redacted from the source documentation.

All SAEs that are unexpected (eg, adverse drug reactions) must be reported to the IRB/IEC as required by ICH GCP E6.

Confirmed pregnancies where conception occurred after first exposure to any IP, and prior to 12 months after last receipt of any IP will be reported to Global PV using the Pregnancy Notification Form. Although normal pregnancy is not an AE, it will mandate discontinuation of IP (refer to [Section 9.4](#)).

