10.3. Analysis Populations

There will be four analysis populations for this study:

The Intent-to-treat (ITT) Population will include all participants who are randomized. Participant disposition and baseline demographics will be summarized by IP group (Groups 1, 2 and 3) for the ITT population according to the group into which the participant is randomized.

The Safety Population will include all randomized participants who receive at least one dose of either antibiotic or AV7909. All the safety analyses will be conducted with the Safety Population according to the treatment they received.

The PK Population will include all participants in Group 1A and Group 2A who:

- Received two doses of AV7909 according to the protocol (eg, correct dose no temperature excursion, and within the study-specified windows)
- If in Group 1A, received at least 5 of the 7 in-clinic ciprofloxacin doses between Day 4 through the morning of Day 8 and between Day 31 through the morning of Day 35; or if in Group 2A, received at least 7 of the 9 in-clinic doxycycline doses between Day 2 through the morning of Day 8 and between Day 32 through the morning of Day 38
- Have adequate data for PK analysis for the calculation of AUC_{0-12h} and C_{max} at the Day 8 (both Group 1A and 2A) and Day 35 (Group 1A) or Day 38 (Group 2A) visits,
- Have no protocol deviations that would affect ciprofloxacin or doxycycline PK

Exclusion of participants from population will be done on a case-by-case basis at the time of the PK parameter analysis.

The PK Population will be used for all PK analyses. Participants will be included in the treatment group (ciprofloxacin or doxycycline) according to the antibiotic they received.

The Immunogenicity Population will include all randomized participants who meet the following criteria:

- Received two AV7909 vaccinations according to the protocol (eg, correct dose, no temperature excursion, and within the study-specified windows)

AV7909 Anthrax Vaccine

IND 014451

Protocol EBS.AVA.210, Version 3.0 (28 October 2019)

- Had a valid immunogenicity (TNA) result at Day 1 (pre-vaccination) showing no evidence of previous exposure to anthrax or an anthrax vaccine (ie, TNA below the limit of detection)
- Had a valid immunogenicity (TNA) result at Day 37, within the study specified window
- Participants in Group 1 or 2 should have taken at least 50% of the protocol-specified antibiotic doses

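### Participants who take antibiotic but leave before vaccination 1 count in 12-month SAE and AESI incidences, yet their planned follow-up ends at the early withdrawal visit

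*Protocol*

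**What the plan says.** **Endpoints.** Protocol 3.2.2 defines "Incidence of serious AEs (SAEs) from the first dose of any IP until the 12-month follow-up" and "Incidence of AESIs from the first dose of any IP until the 12-month follow-up", both to Day 388. Protocol 10.1.2.1 and SAP 2.3.2.1 repeat these windows.

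**Population.** Protocol 10.3 states: "The Safety Population will include all randomized participants who receive at least one dose of either antibiotic or AV7909". SAP 3.2 uses the same definition and then places participants in Group 1, 2 or 3 by treatment received. SAP 8 tabulates all safety data on that basis.

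**Follow-up.** Protocol 6.1.4 deals with Group 1 and 2 participants who cannot be given vaccination 1 because of illness, fever or another condition judged by the investigator. They stop antibiotic, "continue with their e-diary for an additional 7 days beyond the day they ceased taking antibiotics", and then attend the early withdrawal visit (EWV). The section adds: "These participants, having not received any vaccine, will not be included in the long-term follow-up". Protocol 7.3 is wider. It promises efforts to follow participants "through the Month 12 safety follow-up providing they have received at least one vaccination", and it offers those who stop for any reason after antibiotic but before vaccination only the EWV procedures, without the autoantibody, TSH and TNA draws. Protocol 7.3.1 carries the same vaccination condition.

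**Text pointing the other way.** Protocol 7.3.2 asks those who withdraw from study treatment to continue safety evaluations and calls, and that sentence has no vaccination condition. Protocol 9.4 encourages anyone who becomes pregnant after a dose of any product to stay in safety follow-up, again without that condition.

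**Pregnancy.** Protocol 9.3.1 requires immediate reporting of "Any pregnancy where conception occurred after first exposure to any IP" and within 12 months of the last dose. Antibiotics count as product. The routine question about late pregnancies is asked at the quarterly calls in Protocol 8.1.7.

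**The concern.** The endpoint and population definitions start the clock at the first antibiotic dose, whereas the follow-up rule depends on vaccination. A participant who falls between the two belongs to the population for a 12-month incidence but is scheduled to be observed for about two weeks. The SAP has no exposure-time or censoring rule that would show this, so the missing time is reported as free of events.

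The gap arises only in the antibiotic groups. A Group 3 participant who leaves before vaccination has taken no product and is outside the Safety Population. The people concerned may also not be a random subset, because Protocol Table 4 discontinues treatment for the reactions listed in the antibiotic warnings.

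At stake are the meaning of the Month 12 SAE and AESI percentages and the active detection of pregnancies in the reporting window. No safety hypothesis is tested, and the primary PK and immunogenicity analyses are not affected.

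**Working it through.** **1. The plan's own date.** The safety calls are keyed to Day 23: 23 + 365 = 388. Likewise 23 + 91 = 114, 23 + 182 = 205 and 23 + 273 = 296. The stated call days reproduce.

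**2. Share of the endpoint window observed.** Protocol 9.2 gives the first-dose days as "Day 2 for Group 2, Day 4 for Groups 1 or Day 8 for Group 3". Under 6.1.4 the EWV falls 7 days after antibiotic stops.

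- Full window = 388 − first-dose day + 1: doxycycline 388 − 2 + 1 = 387 days; ciprofloxacin 388 − 4 + 1 = 385 days.
- Observed = EWV day − first-dose day + 1.

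| Antibiotic | Stops | EWV | Observed | Share | Not observed |
|---|---|---|---|---|---|
| Doxycycline | Day 8 | Day 15 | 14 of 387 | 3.6% | 373 days |
| Ciprofloxacin | Day 8 | Day 15 | 12 of 385 | 3.1% | 373 days |
| Doxycycline | Day 5 | Day 12 | 11 of 387 | 2.8% | 376 days |
| Ciprofloxacin | Day 5 | Day 12 | 9 of 385 | 2.3% | 376 days |

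The 7-day interval comes from 6.1.4. Section 7.3 gives no timing for the EWV, so exits for other reasons may differ.

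**3. Pregnancy window.** With a last dose on Day 8, twelve months end at about Day 8 + 365 = 373. After an EWV on Day 15, 373 − 15 = 358 days have no planned enquiry.

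**4. Effect on a pooled percentage.** SAP Appendix I takes all participants in the analysis population as the default denominator, and SAP 4.4 summarises observed cases. Suppose k of 70 in an antibiotic group are antibiotic-only, the event rate is constant, events are rare and everyone else is followed to Day 388. Then the relative loss in the crude incidence is (k/70) × (unobserved days / full window).

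- k = 1: (1/70) × (373/387) = 1.4%
- k = 3: 4.1% (doxycycline), 4.2% (ciprofloxacin)
- k = 5: 6.9% in both
- k = 7: 9.6% (doxycycline), 9.7% (ciprofloxacin)

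The documents do not give k. If 2% to 5% of the 140 antibiotic participants leave before vaccination, that is 2.8 to 7 people across both groups, towards the lower end of this range.

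**5. Tables.** Protocol 10.6 lists separate columns for ciprofloxacin only and doxycycline only, beside the two combined columns, AV7909 only, and a total. Under that layout the combined columns are not diluted; only the total is. SAP 3.2 and SAP 8 do not carry the antibiotic-only columns forward, so the dilution in step 4 can return. Even in a separate column, a 12-month incidence would rest on about two weeks of planned observation.

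**The case against.** The strongest reply is that the exclusion is deliberate. Protocol 2.3.2.2 bases 12-month monitoring on the autoimmune risk of the CpG adjuvant, and Protocol 9.1.3 anchors late AESI monitoring to the last vaccination. For antibiotic alone, the 7-day diary is long compared with the half-lives in Protocol 4.3.3: 168 h / 22 h is about 7.6 doxycycline half-lives (fewer if the half-life is longer), and more for ciprofloxacin. This justifies limiting AESI monitoring to vaccinees. It does not justify an endpoint and population that say otherwise.

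A reader might infer that safety and pregnancy information on these people is almost wholly lost. The documents do not support that. The EWV (Protocol 8.1.8) includes a full examination, laboratory tests, a serum pregnancy test and AE review. Under 6.1.4 an event that prevented vaccination is followed until it resolves, stabilises or is referred elsewhere, and Protocol 9.7.2 follows known SAEs and AESIs in much the same way. Known pregnancies are followed to outcome, and later ones remain reportable if the site hears of them.

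A reader might also infer a uniform bar on follow-up. The quoted sentence in 6.1.4 covers only illness, fever or another precluding condition. Section 7.3 is needed to generalise it, and 7.3.2 and 9.4 conflict with it. Within 7.3.2 itself, the item on adverse events does carry a vaccination condition, so that section is not consistent either.

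Finally, it is fair to say that any early withdrawal limits a crude incidence, and that SAP 8.1.3 separately tabulates events starting before vaccination 1. The difference here is that the shortfall is scheduled in the plan and confined to the antibiotic groups.

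**Conclusion.** The point holds in a limited form. For antibiotic-only participants, the plan states a 12-month SAE and AESI incidence that its own follow-up rules do not measure. About 3% to 4% of the window is observed if antibiotic stops on Day 8. What is missing is active enquiry about new SAEs, AESIs and conceptions after the EWV.

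It would go too far to conclude that the Month 12 percentages are materially biased. The number affected is unknown, the 2% to 5% range is an assumption, and the Protocol 10.6 columns would remove the dilution from the combined groups. The effect on percentages is probably small. The dilution figures rest on a constant event rate and on the SAP's Group 1 to 3 layout being applied as written. Two defects need no assumption: the SAP drops the antibiotic-only columns, and the protocol sections on follow-up contradict each other.

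**What to change.** **(a) SAP 3.2, 8 and 8.1.** Restore the antibiotic-only columns of Protocol 10.6. Base the Month 12 SAE and AESI percentages on participants with at least one vaccination. State the shorter observation window that applies to antibiotic-only participants. This costs a few lines of SAP text and table shells.

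**(b) Protocol.** Reconcile 6.1.4, 7.3 and 7.3.1 with 7.3.2 and 9.4, and with the 12-month pregnancy window in 9.3.1 and 9.4. One way is to make the existing 8.1.7 calls to everyone who took any product, with no added visits or blood draws. Section 8.1.7 already keys the calls to the target Day 23 when that visit is missed. At four calls each, the assumed 3 to 7 people would need 12 to 28 calls, plus minor protocol wording. If the calls are adopted, the window stated under (a) for antibiotic-only participants becomes Day 388.
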